4.3.2.2 Oseltamivir-Neuraminidase Inhibitor (NAI)

The Sponsor will supply 75-mg oseltamivir (Tamiflu[®]) capsules for this study for up to a 10-day course (*for 75- or 150-mg BID regimens*). Oseltamivir will be administered twice daily as described in [Section 3.1.1](#). Capsules can be opened and the granules administered via nasogastric tube, if required. Doses should be captured in the eCRF. *For renal dose adjustments, follow local standard-of-care practice/local package insert and document in the eCRF. Capsules other than 75 mg (for 75- or 150-mg BID regimens) cannot be provided through the study IxRS. In these instances, the study site may supply the appropriate dose and be reimbursed by the Sponsor.*

Any overdose or incorrect administration of oseltamivir should be noted on the oseltamivir Administration eCRF. AEs associated with an overdose or incorrect administration of oseltamivir should be recorded on the Adverse Event eCRF.

Patients who are discharged from the hospital with oseltamivir will be required to complete a medication diary and return the medication diary, empty (used) oseltamivir packets and unused oseltamivir capsules to the study site at the next follow up visit. Patients will record the date and time when each oseltamivir capsule is administered.

4.3.3 Investigational Medicinal Product Accountability

Investigational medicinal products (IMPs) required for completion of this study (i.e., MHAA4549A and 75-mg oseltamivir capsules) will be provided by the Sponsor. The

study site will acknowledge receipt of IMPs and confirm the shipment condition and content. Any damaged shipments will be replaced.

The IMP will be stored in a secure pharmacy or locked area with access limited to authorized personnel, in accordance with the details provided in the Investigator's Brochure and Pharmacy Manual. Upon receipt, MHAA4549A and placebo vials must be refrigerated at 2°C to 8°C until use. MHAA4549A does not contain antimicrobial preservatives; therefore, care must be taken to ensure that the solution for infusion is not microbiologically compromised during preparation. Dilute under appropriate aseptic conditions using 0.9% normal saline. The solution for infusion should be used immediately. If not used immediately, in-use storage times and conditions prior to use should not exceed 24 hours at 2°C to 8°C and/or 4 hours at ambient temperature (18°C–24°C). If the dose solution is stored at 2°C–8°C, it should be removed from refrigeration and allowed to reach room temperature prior to administration. If the infusion is interrupted and the combined ambient temperature storage and interruption time exceeds 4 hours, prepare a new dose solution to resume the infusion (see the Pharmacy Manual). Protect dose solutions from heat and intense light.

The total duration from the preparation of dose solutions to the end of infusion should not exceed 24 hours. Vials are intended for single use only; therefore, any remaining solution should be discarded (see the Pharmacy Manual).

IMPs will either be disposed of at the study site according to the study site's institutional standard operating procedure or returned to the Sponsor or their delegate with the appropriate documentation. The site's method of IMP destruction must be agreed to by the Sponsor. The site must obtain written authorization from the Sponsor before any IMP is destroyed, and IMP destruction must be documented on the appropriate form.

Accurate records of all IMPs received at, dispensed from, returned to, and disposed of by the study site should be recorded on the Drug Inventory Log.

4.4 POST-TRIAL ACCESS TO MHAA4549A

As this is single dose administration, Genentech does not intend to provide MHAA4549A to patients after the conclusion of the study or any earlier withdrawal. Patients may or may not be eligible for any potential subsequent trials of MHAA4549A under a separate protocol.

The Roche Global Policy on Continued Access to Investigational Medicinal Product is available at the following Web site:

http://www.roche.com/policy_continued_access_to_investigational_medicines.pdf

4.5 CONCOMITANT THERAPY AND FOOD

Concomitant medication includes any medication (e.g., prescription drugs, over the counter drugs, herbal or homeopathic remedies, nutritional supplements) used by a patient from 30 days prior to screening to the study completion/*early* discontinuation visit. All concomitant medications should be reported to the investigator and recorded on the Concomitant Medications eCRF. For any NAIs (e.g., oseltamivir, peramivir, zanamivir, laninamivir) that have been taken prior to study drug therapy, the number of doses and duration of therapy must be recorded.

4.5.1 Permitted Therapy

Patients who use oral contraceptives, hormone-replacement therapy, or other maintenance therapy should continue their use.

All therapies required for management of the patient's acute illness are permitted except for those listed below in [Section 4.5.2](#).

4.5.2 Prohibited Therapy

Use of the following therapies is prohibited during the study and for at least 7 days prior to study treatment, unless otherwise specified below: probenecid, amantadine, or rimantidine.

Use of other NAIs, including but not limited to oseltamivir, zanamivir, *laninamivir*, and peramivir, are prohibited during the study, but allowed up to a total of 6 doses (3 doses for peramivir) in the period from onset of symptoms and prior to study treatment as outlined in the exclusion criteria. Patients must start standard-of-care oseltamivir no later than 12 hours after completion of MHAA4549A administration. If oseltamivir resistance is highly suspected or identified or if oseltamivir route of administration challenges are encountered then, following discussion with the Sponsor's *Medical Monitor*, an alternative NAI to oseltamivir may be used.

4.5.3 Prohibited Food

There are no prohibited foods for this study.

4.6 STUDY ASSESSMENTS

Please see [Appendix 1a](#) and [Appendix 1b](#) for the schedule of activities performed during the study.

4.6.1 Informed Consent Forms and Screening Log

Written informed consent for participation in the study must be obtained before performing any *study-related procedures*. Informed consent by authorized representatives may be obtained only if allowed by and in accordance with local regulations and Independent Review Board (IRB)/Independent Ethics Committee (IEC)

policies and procedures. Informed Consent Forms (ICF) for enrolled patients and for patients who are not subsequently enrolled will be maintained at the study site.

All screening evaluations must be completed and reviewed to confirm that patients meet all eligibility criteria before randomization. The investigator will maintain a screening log to record details of all patients screened and to confirm eligibility or record reasons for screening failure, as applicable.

4.6.2 Diagnostic Testing for Enrollment

All hospitalized patients with severe influenza A must be assessed for disease confirmation prior to and enrollment into the study. A Sponsor-approved influenza test is required as an aid in the diagnosis of influenza A infection. This requires a nasopharyngeal swab be introduced into one nostril. *A lower respiratory tract sample may be used if appropriate for the Sponsor-approved local PCR test.* Note that the influenza antigen test or influenza PCR test result must be available within the 48-hour screening window.

4.6.3 Medical History and Demographic Data

Medical history includes clinically significant diseases and procedures, including chronic respiratory disease, infections, surgeries, cancer history (including prior cancer therapies and procedures), reproductive status, smoking history, use of alcohol and drugs of abuse, and all medications (e.g., prescription drugs, over-the-counter drugs, herbal or homeopathic remedies, nutritional supplements) used by the patient within 30 days prior to the screening visit. A careful assessment of the patient's baseline SpO₂ will be made especially if the patient has a history of severe chronic lung disease.

Demographic data will include age, sex, and self-reported race/ethnicity.

4.6.4 Priority of Assessments

When events warrant, or in the opinion of the investigator, safety issues become paramount, safety assessments will always have priority over all other measurements and procedures. Under routine circumstances, however, PK, nasal virological, and biomarker serum/plasma samples have priority over other measurements. The timing and number of safety measurements may be modified based on clinical evaluations.

Assessments on Day 1 must be concluded prior to dosing as specified in [Appendix 1a](#). Any screening assessments completed prior to consent as standard of care do not need to be repeated if done within the screening period.

4.6.5

[REDACTED]

4.6.6

[REDACTED]

4.6.7 Physical Examinations

A complete physical examination should include an evaluation of the head, eyes, ears, nose, and throat, and the cardiovascular, dermatological, musculoskeletal, respiratory, gastrointestinal, genitourinary, and neurological systems. Any abnormality identified at baseline should be recorded on the General Medical History and Baseline Conditions eCRF.

At protocol designated visits (or as clinically indicated), limited, symptom-directed physical examinations should be performed which include, at a minimum, evaluation of general appearance, dermatological examination of the injection sites, evaluations directed by patient-reported symptoms, and any other evaluations that the investigator deems clinically relevant. Changes from any prior examination should be recorded. New or worsened abnormalities should be recorded as AEs, if appropriate, on the adverse event eCRF.

Day 1 physical examination is optional if already completed on Day -1 or -2.

4.6.8 Vital Signs

Vital signs will include measurements of respiratory rate, *heart* rate, temperature, and systolic and diastolic blood pressures after the patient has been in a seated or supine position for >5 minutes. *Temperature should be measured using the same methodology throughout the study and should be measured prior to administration of any antipyretic drugs.* Patients in intensive care may have vital signs assessed following local procedures, but those procedures should be captured in the eCRF in accordance with the eCRF instructions.

4.6.9 Oxygen Saturation Measurements

To ensure that the respiratory status is well recorded, the following daily measurements will be performed. *All* patients will have their SpO₂ and corresponding respiratory

assessments recorded daily in the morning between 6:00 a.m. and 12:00 noon local time. *Unless clinically contraindicated**, patients on low flow O₂ will have a daily trial of their SpO₂ while on and off the supplementation, as outlined in [Appendix 2](#), and both values will be recorded. If a patient is clinically able to be removed from oxygen outside the time window above (6:00 a.m. to 12:00 noon), the trial-off data should be recorded as an unscheduled visit.

If the patient is on oxygen supplementation, SpO₂ measured by pulse oximetry and the corresponding respiratory assessments (e.g., FiO₂, flow rate) will be recorded. If the patient is on PPV, partial pressure of arterial O₂ (PaO₂) and the corresponding respiratory assessments (e.g., FiO₂, ventilator mode, ventilator respiratory rate, positive end expiratory pressure) will be recorded. If clinically appropriate (i.e., the patient is on non-invasive PPV), the conversion table in [Appendix 11](#) may be used for PaO₂.

**If a patient has an SpO₂ <95% while on oxygen supplementation, he/she shall be considered to be “clinically contraindicated” from requiring a trial off oxygen; however, corresponding respiratory assessments should be recorded.*

4.6.10 Laboratory, Biomarker, and Other Biological Samples

Samples for the laboratory tests listed in [Table 3](#) and [Table 4](#) will be sent to the study site's local laboratory for analysis at screening and during the study, respectively.

Table 3 Laboratory Tests at Screening

Hematology:	Clinical Chemistry:
Hemoglobin	Thyroid stimulating hormone (optional)
Hematocrit	
Erythrocyte count (RBC)	Serology:
Leukocytes (WBC)	HIV Serology
Neutrophils (segmented and bands if clinically indicated)	
Lymphocytes	Misc:
Monocytes	Pregnancy Test (urine or serum; women of child-bearing potential)
Eosinophils	
Basophils	
Platelets	

Note: Investigators must document their review of each laboratory report by signing (or initialing) and dating each report.

Table 4 Laboratory Tests during the Study

Hematology:	Clinical Chemistry (Blood):
Hemoglobin	Sodium
Hematocrit	Potassium
Erythrocyte count (RBC)	Bicarbonate
Leukocytes (WBC)	Chloride
Neutrophils (segmented and bands if clinically indicated)	Calcium
Lymphocytes	Phosphorus
Monocytes	Magnesium
Eosinophils	Glucose
Basophils	Urea nitrogen (BUN) or urea
Platelets	Creatinine
	Total cholesterol
	Total protein
Coagulation:	Albumin
Activated partial thromboplastin time (APTT)	Total bilirubin
Prothrombin time (PT)	Alkaline phosphatase
International Normalized Ratio (INR)	Aspartate aminotransferase (AST)
	Alanine aminotransferase (ALT)
Urinalysis:	Amylase
pH	Gamma-glutamyl transpeptidase (GGT) (if clinically indicated)
Specific gravity	
Glucose	C-reactive protein (CRP) (optional)
Protein	Erythrocyte Sedimentation Rate (ESR) (optional)
Ketones	
Blood	
Bilirubin	Misc:
Nitrite	Pregnancy Test (urine or serum ; if clinically indicated)
Leukocyte esterase	
Microscopic examination (if clinically indicated)	

Note: Investigators must document their review of each laboratory report by signing (or initialing) and dating each report.

The following samples will be sent to the Sponsor or a designee for PK or ATA analysis:

- █ [REDACTED]
- Serum samples for ATA testing (see [Appendix 1a](#) and [Appendix 1b](#))
- █ [REDACTED]
- █ [REDACTED]
- █ [REDACTED]
- █ [REDACTED]
- █ [REDACTED]

For sampling procedures, storage conditions, and shipment instructions, see the laboratory manual.

4.6.11 Electrocardiograms

Single ECG recordings will be obtained at specified timepoints, as outlined in the schedule of *activities* (see [Appendix 1a](#) and [Appendix 1b](#)), and may be obtained at unscheduled timepoints as indicated.

All ECG recordings must be performed using a standard high-quality, high-fidelity digital electrocardiograph machine equipped with computer-based interval measurements. Lead placement should be as consistent as possible. ECG recordings must be performed after the patient has been resting in a supine position for at least 10 minutes. All ECGs are to be obtained prior to other procedures scheduled at that same time (e.g., vital sign measurements, blood draws) and, *if possible*, should not be obtained within 3 hours after any meal. Circumstances that may induce changes in heart rate, including environmental distractions (e.g., television, radio, conversation) should be avoided during the pre ECG resting period and during ECG recording.

For safety monitoring purposes, the investigator must review, sign, and date all ECG tracings. Paper copies of ECG tracings will be kept as part of the patient's permanent study file at the site. The following should be recorded in the appropriate eCRF: HR, RR interval, QRS interval, PR duration, uncorrected QT interval, and QTcF (*or QTcB if*

QTcF is not available) based on the machine readings of the individual ECG tracings. Any morphologic waveform changes or other ECG abnormalities must be documented on the eCRF. If considered appropriate by the Sponsor, ECGs may be analyzed retrospectively at a central laboratory.

If at a particular postdose timepoint the mean *corrected QT interval* is >500 ms and/or >60 ms longer than the baseline value, another ECG must be recorded, ideally within the next 5 minutes, and ECG monitoring should continue until *the corrected QT interval* has stabilized on two successive ECGs. The Medical Monitor should be notified. Standard of care treatment may be instituted per the discretion of the investigator. If a PK sample is not scheduled for that timepoint, an unscheduled PK sample should be obtained. A decision on discontinuation should be made, as described in [Section 4.9.2](#). The investigator should also evaluate the patient for potential concurrent risk factors (e.g., electrolyte abnormalities, medications known to prolong the QT interval, severe bradycardia).

4.6.12

[Redacted text block]

[Redacted text block]

[Redacted text block]

[REDACTED]

[REDACTED]

[REDACTED]

[REDACTED]

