3.3.3 Secondary Efficacy Outcome Measures

The secondary efficacy outcome measures for this study are as follows:

- *Clinical status of patient at Days 1–7, 14, and 30. This is an ordinal outcome with six mutually exclusive categories:*
 1. *Death;*
 2. *In the ICU;*
 3. *Non-ICU hospitalization, requiring supplemental oxygen;*
 4. *Non-ICU hospitalization, not requiring supplemental oxygen;*
 5. *Not hospitalized, but unable to resume normal activities; or*
 6. *Not hospitalized with full resumption of normal activities*
- Clinical failure after 24 hours post-infusion of study drug; defined as:
 - Progression to increased O₂ requirement defined by an increase in oxygen supplementation from low flow oxygen (i.e., 2–6 L/min) to high flow oxygen

(i.e., >6 L/min) or from oxygen supplementation alone to any PPV or extracorporeal membrane oxygenation (ECMO)

- Progression to ICU
- Prolonged ventilation or O₂ support defined by >2 weeks, or
- Death
- Time to clinical resolution of *abnormal* vital signs (3/5 criteria must be met):
 - SpO₂ ≥ 95% without supplemental O₂
 - Respiratory rate < 24 breaths per minute without supplemental O₂
 - Core temperature < 37.2°C immediately prior to receipt of any antipyretic drug, and at least 6-8 hours from the last dose of antipyretic or core temperature > 36°C in patients who are initially hypothermic
 - Heart rate (HR) < 100 beats/minute
 - Systolic blood pressure (SBP) > 90 mmHg
- All-cause mortality at Day 14, Day 30, and Day 60
- Influenza A viral load in nasopharyngeal samples
 - AUEC (qPCR)
 - Peak viral load (qPCR)
 - *Duration of viral shedding* (qPCR)
- Duration of hospitalization
- Duration of ICU stay
- Antibiotic usage for respiratory infections
- Complications of influenza:
 - Pneumonia (HAP/VAP)
 - Exacerbations of chronic lung disease
 - Myocarditis
 - ARDS
 - Otitis media
 - Other related complications
- All-cause readmission at Day 30 and Day 60
- Duration of ventilation

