6.3 SUMMARIES OF TREATMENT GROUP COMPARABILITY

Demographic and baseline characteristics of the patient will be summarized for all randomized patients by treatment group by use of descriptive statistics. Baseline is defined as the last available value prior to study drug administration.

During the study patient disposition, concurrent treatment, and compliance with study treatment and visits will be summarized on the safety analysis population using descriptive statistics.

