Appendix 1a Schedule of *Activities*

Notes: Unless otherwise indicated, **all assessments on Day 1 should be performed prior to study drug administration**; x's within parentheses, i.e., (x), indicate optional assessments. Please refer to Follow-up Period table for visits to be completed after patient is discharged from hospital prior to Day 60. Any screening assessments completed prior to consent as standard of care do not need to be repeated if done within the screening period. If a patient is unable to be present at the site for a follow-up visit, a telephone visit is *encouraged*.

Hospitalized Days (only to be completed while patients are hospitalized)																						
	D -2,-1	D1 (Randomization)	D2	D3	D4	D5	D6	D7	D8	D9	D10	D11-13	D14	D15-19	D20	D21-24	D25	D26-29	D30	Hospital Discharge ^a	D60 Study Completion or Early Discontinuation while hospitalized	Unscheduled
Informed consent ^b	x																					
Sponsor-approved influenza test ^c	x																					
Inclusion/exclusion criteria	x																					
Medical history and demographic	x																					

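### Where the ECG machine prints no QTcF, the QT action limits in section 4.6.11 run on QTcB and so move with heart rate; QTcF could be calculated on the spot from the recorded QT and RR

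*Combined protocol and SAP*

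**What the plan says.** Section 4.6.11 (Version 7) lists the eCRF entries for each ECG: "HR, RR interval, QRS interval, PR duration, uncorrected QT interval", and QTcF, with QTcB accepted where QTcF is not available. All are "based on the machine readings of the individual ECG tracings".

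The action rule follows. If the corrected QT at a post-dose timepoint "is >500 ms and/or >60 ms longer than the baseline value, another ECG must be recorded", "ideally within the next 5 minutes". Monitoring then continues until the interval settles on two ECGs in a row. The Medical Monitor is told, an unscheduled PK sample is drawn if none is due, a discontinuation decision is made, and the investigator looks for risk factors, among them "medications known to prolong the QT interval, severe bradycardia".

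The rule refers only to a corrected QT and names no formula. The Version 7 summary of changes shows this general term being put in place of QTcF in that sentence, which supports reading the rule as covering either formula. Nothing tells sites to calculate QTcF, and nothing requires the same formula at baseline and post-dose.

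On timing, section 6.3 states: "Baseline is defined as the last available value prior to study drug administration". Appendix 1a adds that, unless otherwise indicated, "all assessments on Day 1 should be performed prior to study drug administration". The baseline ECG is therefore the Day 1 pre-dose tracing. Scheduled post-dose ECGs fall on Days 5, 14, 30 and 60 and at discharge.

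**The concern.** Bazett's and Fridericia's corrections agree only at 60 bpm. A fixed limit on QTcB is therefore a different limit on QTcF at every other heart rate, and a fixed change limit shifts whenever heart rate differs between baseline and post-dose.

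Two directions could do harm:

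- **Slow heart rate.** QTcB reads low, so a QTcF above 500 ms can pass, although the same section names severe bradycardia as a QT risk factor.
- **Falling heart rate.** Baseline is taken in acute illness and later ECGs during recovery. Section 3.3.3 counts "Heart rate (HR) < 100 beats/minute" among its criteria for resolution of abnormal vital signs, so slowing is anticipated. It lowers QTcB with no change in QTcF and can hide a true rise above 60 ms.

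A missed trigger means that none of the follow-up steps is prompted. In the other direction, tachycardia produces false alarms. Above 60 bpm the 500 ms limit errs on the safe side.

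**Working it through.** There is no derived figure in the plan to reproduce; 500 ms and 60 ms are set limits.

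**Inputs from the protocol:** the two limits, the QTcB fallback, and the recording of QT and RR (section 4.6.11).

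**Assumed, not in the documents:** baseline QTcF 400–440 ms, baseline heart rate 80–120 bpm, post-dose heart rate 60–80 bpm. Rates of 40 and 50 bpm are added to show the bradycardia direction.

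**Formulas** (standard; the protocol only names them), RR in seconds = 60/HR:

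- QTcF = QT/RR^(1/3) and QTcB = QT/RR^(1/2)
- so QTcB = k × QTcF, with k = (HR/60)^(1/6)

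**1. The 500 ms limit when QTcB is used.** The equivalent QTcF is 500/k.

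| HR | k | QTcF at QTcB = 500 ms |
|---|---|---|
| 40 | 0.9347 | 535 |
| 50 | 0.9701 | 515 |
| 60 | 1 | 500 |
| 70 | 1.0260 | 487 |
| 80 | 1.0491 | 477 |
| 100 | 1.0889 | 459 |
| 120 | 1.1225 | 445 |

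At 50 bpm a QTcF of 510 reads 510 × 0.9701 = 494.7 ms and does not fire. At 110 bpm a QT of 370 ms gives QTcB 501 ms, which fires, but QTcF 453 ms, which would not.

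**2. The 60 ms limit with QTcB at both times, baseline HR 100.** With QTcF unchanged at 400 ms, QTcB moves by 400 × (k_post − 1.0889): −15.9 ms at post-dose HR 80, −25.1 ms at 70 and −35.5 ms at 60.

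Example, HR 100 to 70, QTcF 400 to 470: 470 × 1.0260 − 400 × 1.0889 = 482.2 − 435.5 = +46.7 ms. Neither limit fires on a true rise of 70 ms.

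With both limits in play and baseline QTcF = Q, the true rise at which the rule fires is

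min[(Q × k_base + 60)/k_post, 500/k_post] − Q.

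| Q (ms) | Post-dose HR 80 | HR 70 | HR 60 |
|---|---|---|---|
| 400 | 72.3 | 83.0 | 95.5 |
| 420 | 56.6 | 67.3 | 80.0 |
| 440 | 36.6 | 47.3 | 60.0 |

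Entries above 60 are missed rises. At Q = 440 nothing is missed.

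The ends of the assumed baseline heart-rate range, at Q = 400:

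- Baseline HR 80: QTcB is 419.6 ms. The rule fires at rises of 57.2, 67.5 and 79.6 ms (post-dose HR 80, 70, 60).
- Baseline HR 120: QTcB is 449.0 ms, and adding 60 exceeds 500, so the 500 ms limit governs. The rule fires at 76.6, 87.3 and 100 ms.

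**3. Only if the formula differs between times** (QTcB at baseline, QTcF later). The 60 ms limit shifts by Q × (k − 1). At baseline HR 80, 100 and 120 that is 19.6, 35.5 and 49.0 ms for Q = 400, and 20.6, 37.3 and 51.4 ms for Q = 420. The rule fires at min(Q × k + 60, 500) − Q: 79.6, 95.5 and 100 ms for Q = 400; 80 ms throughout for Q = 420; 60 ms for Q = 440, so nothing is missed there.

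**The case against.** The algebra is not in dispute; the case against is about reach and consequence.

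- **Reach.** QTcF is the preferred measure, QTcB only a fallback, and the section asks for good digital machines with computed intervals. The share of ECGs affected could be close to zero. That stands: the documents give no figure.
- **Assumptions.** Every heart rate and baseline QTcF is assumed, and one heart-rate criterion among five does not show that patients arrive tachycardic. That also stands. Missed 500 ms readings need a heart rate below 60, outside the assumed post-dose range. The milder baseline rate of 80 narrows the gap, while 120 widens it.
- **Severity of what is missed.** In part 2 every missed rise leaves QTcF at or below 500 ms. The drug is a single infusion, finished before the scheduled post-dose ECGs, and three earlier studies reported no ECG concern (section 1.2.2). This lowers the stakes, although those studies were in healthy volunteers.
- **Mixed formulas.** Like for like is the natural reading, so part 3 is secondary.
- **Safeguards.** The investigator reviews and signs every tracing, and QTcF can be derived later from the eCRF. Central reading is optional and retrospective. None of these resets the trigger at the time, and the reviewer has no QTcF to look at unless someone calculates it.
- **Burden.** A machine-read fallback is practical across about 170 centers, and a hand calculation can go wrong. A lookup table limits that risk.

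**Conclusion.** The concern holds as a minor safety-monitoring point. As written, any ECG without a machine QTcF is judged on QTcB, and the effective limits then depend on heart rate. Under the stated assumptions, with baseline heart rate 100 and QTcB at both times, true QTcF rises above 60 ms go unflagged up to 72, 83 or 96 ms at baseline QTcF 400 (post-dose rates 80, 70, 60), and up to 67 or 80 ms at baseline 420 (rates 70, 60). None is missed at 420 with rate 80, or at 440. Below 60 bpm the 500 ms limit is also too lax.

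This rests on assumed heart rates and baseline QTcF, and on an unknown number of sites without QTcF. There is no effect on power or on any efficacy analysis.

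**What to change.** Amend section 4.6.11 so that, where the machine does not print QTcF, the site calculates QT/RR^(1/3) (RR in seconds) at the time of the ECG, for the baseline and every post-dose tracing. Apply both limits to QTcF only and remove the QTcB fallback. Requiring merely the same formula as at baseline would deal with part 3 of the working but leave parts 1 and 2 untouched.

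The cost is protocol wording plus a brief bedside calculation or lookup table at the sites concerned. No additional ECGs or data fields are needed, since QT and RR are already captured.
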